## **D4. Study Recruitment**

Since participation of the adolescent's therapist is required in order for a parent-youth dyad to be eligible for the study, therapists will be recruited first. Once enrolled, participating therapists will then assist in the recruitment of eligible parent-youth dyads from their existing caseloads. We seek a final sample size of no less than 24 therapist-parent-youth triads (i.e., 72 individual participants) who complete all study procedures. To account for potential premature participant dropout (e.g., youth is incarcerated in week 2; parent loses mobile phone service due to unpaid bills), we plan to enroll  $N = 30$  therapist-parent-youth triads. These triads will be allocated between the field test ( $n = 4-6$  triads) and the open trial ( $n = 20$ ).

Within each triad, all 3 participants must agree for any individual in the triad to complete study procedures. Among enrolled triads, all parent-youth dyads must be unique, but their linked therapist participants do not. If a given enrolled therapist's caseload yields more than one parent-youth dyad also enrolled, that therapist will be linked to more than one parent-youth dyad in the study. Thus, while the final sample size will be no less than  $n = 24$  parents and  $n = 24$  youth, it is possible that the number of enrolled therapists will be lower (e.g.,  $n = 12$  therapists, if each therapist had two parent-youth dyads from her caseload enrolled).

Conversely, we expect that for some enrolled therapists, we will be unsuccessful in recruiting any linked parent-youth dyads from their caseloads (due to disinterest in the study or ineligibility). To account for this possibility, we will continue to recruit and enroll therapists until an  $N$  of 24 parent-youth dyads completed is achieved. One implication of this approach is that more therapists may be enrolled in the study than will actually have the opportunity to engage in study procedures (e.g., we may need to enroll  $N = 40$  therapists to achieve  $N = 24$  parent-youth dyads).

The recruitment procedures that follow are informed by experiences recruiting therapists and having therapists refer parents and youth to the study during the formative evaluation of VW (previous protocol). As described below, two separate lottery drawings (one for therapists, one for parents/youth) will be used as one part of a more comprehensive recruitment strategy.

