Once both parent and youth baseline sessions are complete, the parent will receive a thank-you card by mail, thanking the family for completing the baseline assessment and informing them that \$35 compensation has been banked for them for the sessions (\$25 for parents, \$10 for youth; see below). The note will also remind parents that payment may take the form of a check made out to the parent or retention of the study-provided phone, and will be provided at the end of study procedures.

**Downloading the app.** Once both baseline sessions are complete, the parent and youth each will receive an email with a link to the VillageWhere server and his/her study-created password. The parent's activation email will be sent only to the parent; the youth's activation email will be sent to the youth and parent. Both activation emails will be sent immediately after both have completed the baseline assessment; participants will click on the link using their smartphone, enter their email address and password, and click to download the app. After this procedure is explained to the parent, the research assistant will offer to assist the parent or youth in downloading the app if desired, either immediately or in a subsequent phone call.

Research staff will monitor whether or not each participant has downloaded the app by looking on the server. If after one week of sending the initial activation email the participant has not downloaded the app, the research assistant will remind the participant to do so on day 7 (first reminder email) and every other day thereafter (days 9, 11, and 13) by email. If by day 14 the participant has still not downloaded the app, the research person will make two phone calls and two text message attempts to reach the participant during days 14-21. Participants who have not downloaded the app within 21 days of the baseline assessment session will be administratively withdrawn from the study.

The dyad's (parent and youth) app usage testing period will be considered to begin on the next calendar day after the second dyad member's app is downloaded (i.e., after whomever's app – parent's or youth's - is downloaded last).

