## **D11. Data Analysis**

Data from demographics questionnaires and the Technology Use and Comfort Survey will be used to describe the sample itself. App usage and SUS data will be used to describe the success of the app itself. On the SUS, scores below a 3.5 on a five-point Likert scale (1 = poor; 2 = fair; 3 = good; 4 = very good; 5=excellent) will indicate a need for further app refinement in subsequent research. An aggregated mean score of 3.5 or higher will support app feasibility. App usage data will be aggregated and subjected to descriptive analyses to determine most preferred features and feature use sequences. Correlational analyses will link app usage data to participant satisfaction ratings and to measures of parent/youth behavior and functioning, to determine if certain app features were more highly preferred or more linked to changes in functioning than others.

Average scores on the SUS will also be compared between parents and adolescents. Between-group comparisons on the USAS will involve independent samples t-tests; effect size estimates also will be computed.

Pre- to post-usage change will be assessed on all parent and youth measures of functioning and behavior. Paired-samples T tests will be used and effect sizes obtained.

Qualitative data obtained from exit interviews will include annotations from investigators noting likes, dislikes, points of confusion, suggestions for improvement, misunderstandings, and potential unintended consequences. Qualitative data will be analyzed using a grounded theory approach (a data-reduction method for qualitative data used to generate and test hypotheses from the ground up).

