## **E. PROTECTION OF HUMAN SUBJECTS**

### **E1. RISKS TO THE SUBJECTS**

#### *a. Human Subjects Involvement and Characteristics*

- Describe the proposed involvement of human subjects.

- Describe the characteristics of the subject population, including their anticipated number, age range and health status.

Three categories of human subjects will participate: 1) Parents of adolescents who are receiving mental health treatment, 2) adolescents receiving mental health treatment, and 3) therapists providing mental health treatment to parents and adolescents jointly. Participants will include at least 24 parents and 24 youth (at least 4 each in the field-based beta testing phase, 20 each in the Open Trial). Depending on problems encountered during the field test phase of the study, additional parents and youth might be needed to “debug” app problems prior to the open trial. The maximum number of parent and youth enrollees will not exceed 30 of each. Estimating therapist enrollment is difficult, because it is not yet known how many therapists will need to enroll in order to recruit a minimum of  $N = 24$  parent-youth dyads. We assume that a maximum  $N = 40$  enrolled therapists will be sufficient to recruit the parent-youth sample.

Parent and therapist age ranges will vary, but all will be adults (age 18 or older). Youth participants will range in age from 12-17 years old. All participants are expected to be physically healthy. In terms of mental health functioning, adolescent participants will be heterogenous, but all will have functional impairments sufficient to warrant their participation in either in-home or outpatient mental health treatment. Functional impairments may include internalizing symptoms (e.g., depressed mood, anxiety, social withdrawal), externalizing symptoms (e.g., oppositional behavior, drug or alcohol use), and failure to meet the developmental demands of their natural environments (e.g., to attend school, interact appropriately with peers, or refrain from criminal activity). A unifying factor across this heterogenous sample of adolescents is that all will be receiving family-oriented mental health treatment in which one goal is improved parental management of adolescent behavior.

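### D11 compares parent and adolescent SUS scores with an independent-samples t-test, although the two groups are parent-youth pairs from the same families

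*Combined protocol and SAP*

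**What the plan says.** D11 (Data Analysis) sets up the comparison: "Average scores on the SUS will also be compared between parents and adolescents". It then names the test: "Between-group comparisons on the USAS will involve independent samples t-tests; effect size estimates also will be computed". The acronym USAS is not defined, and in context it can only sensibly be the SUS.

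The sections on design make these two groups matched pairs:

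- D4 on uniqueness: "Among enrolled triads, all parent-youth dyads must be unique, but their linked therapist participants do not".
- D4 on joint participation: "Within each triad, all 3 participants must agree for any individual in the triad to complete study procedures".
- D6.1 gives the family one shared clock. The dyad's "app usage testing period will be considered to begin on the next calendar day after the second dyad" member has downloaded the app.
- Tables D6.2a and D6.2b give the 10-item SUS to both parent and youth, at post-test only.

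D11 does use paired tests, but only for pre- to post-usage change: "Paired-samples T tests will be used and effect sizes obtained". No section gives a paired or dyad-aware analysis of the parent-adolescent contrast, or a reason to treat the two members of a family as independent.

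**The concern.** The independent-samples t-test takes the variance of the difference in means to be the sum of the two groups' variances. For matched pairs that omits the covariance. If parent and child tend to agree about the app, the planned standard error is too large: the confidence interval is too wide and power is lost. If they tend to disagree, for instance because the parent values monitoring that the youth resents, the standard error is too small and false positives exceed the nominal rate. The documents do not establish either direction.

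This is the only planned test of whether the two kinds of user differ in acceptability, and section E3 lists the app's appeal to youth among the things the study seeks to learn. With 20 to 30 dyads there is little precision to give away.

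**Working it through.** **Inputs from the documents.** 20 open-trial dyads (D6.1); at least 24 dyads in all (D4, section E1); and an upper limit in E1: "The maximum number of parent and youth enrollees will not exceed 30 of each". D11 gives no alpha, SD, effect size or within-dyad correlation for this test, so there is no figure of the plan's own to reproduce.

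**Assumptions.** Two-sided 5% level, equal SDs, bivariate normal scores, complete pairs, dyads independent of one another, r from -0.2 to 0.5, and a true difference of 0.6 SD for power.

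**Formula.** With n dyads and common SD s:

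- true variance of the mean difference: 2s²(1 − r)/n
- variance assumed by the planned test: 2s²/n
- ratio of true to assumed standard error: √(1 − r)
- large-sample type I error: 2[1 − Φ(1.96/√(1 − r))]

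At r = -0.2: 1.96/√1.2 = 1.79, giving 7.4%. At r = 0.3: 1.96/√0.7 = 2.34, giving 1.9%. At r = 0.5: 1.96/√0.5 = 2.77, giving 0.6%. Only r = 0 returns 5%.

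**Simulation, 24 dyads** (400,000 replicates per cell for type I error, 200,000 for power; pooled t on 46 df against paired t on 23 df):

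| r | Type I error, planned test | Power, planned | Power, paired |
|---|---|---|---|
| -0.2 | 7.3% | – | – |
| 0 | 5.0% | 53% | 51% |
| 0.1 | 3.9% | 53% | 55% |
| 0.3 | 2.1% | 54% | 66% |
| 0.5 | 0.7% | 54% | 80% |

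The paired test's type I error was 4.9% to 5.0% throughout. No power is shown at r = -0.2, because the planned test's apparent advantage there comes from exceeding its level.

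**Other sample sizes, power at 0.6 SD, planned against paired.**

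- 20 dyads: 45% against 58% at r = 0.3; 44% against 72% at r = 0.5.
- 30 dyads: 65% against 77% at r = 0.3; 67% against 89% at r = 0.5.

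**Smaller effect.** A separate simulation at 0.5 SD (100,000 replicates per cell), at r = 0.3, gave 31% against 44% with 20 dyads and 38% against 51% with 24.

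**Precision, 24 dyads.** The mean 95% confidence interval half-width is 0.58 SD unpaired, against 0.49 SD paired at r = 0.3 and 0.42 SD at r = 0.5.

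**The case against.** The strongest reply is that little rests on this test. No alpha, power or decision rule is attached to it. With complete pairs the mean difference is unbiased, and the feasibility rule, "An aggregated mean score of 3.5 or higher will support app feasibility", does not use it. That stands, and it limits the weight of the point.

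A second reply is that the planned test is conservative, not invalid, when r is positive, and that r may be near zero because parent and youth use different versions of the app (section C). The direction is right, and the size of the loss does depend on assumed values: at r = 0.1 pairing gains only 2 points of power. But the trade is lopsided. Pairing loses about 2 points at r = 0 and gains 12 at r = 0.3 and 26 at r = 0.5. Being conservative is also no virtue in a pilot that is looking for what needs refinement.

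Third, sample size. D6.1 makes the 20 open-trial dyads the main basis for conclusions, and the field-test dyads had 14 days of use and different instructions. Thirty is an enrolment ceiling, while D4 allocates only 4 to 6 plus 20, that is 24 to 26 triads. So the 20- and 24-dyad figures are the relevant ones, and 30 is an upper bound.

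Fourth, the paired test assumes independent dyads, yet D4 allows one therapist to serve several. With D4's own example of 12 therapists with two dyads each, and an assumed therapist intraclass correlation of 0.1 to 0.2 in the within-dyad differences, the paired test's type I error rises to between 6.0% and 7.3%. That is a fair limit on the remedy. It is no argument for the independent test, which ignores therapist clustering as well as the pairing.

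**Conclusion.** The point holds. D11 applies a test for independent groups to data that are matched 1:1 by design, and nothing elsewhere corrects it. The nominal error rate is exact only at zero within-dyad correlation; the test is conservative above zero and anti-conservative below it. Over r from -0.2 to 0.5 with 24 dyads, true type I error runs from 7.3% down to 0.7%. At 0.6 SD the power forgone is 12 points at r = 0.3 and 26 points at r = 0.5. These sizes are illustrative, because r and the effect size are assumed; the mismatch itself needs no assumption beyond reading USAS as the SUS. It should be fixed, but it concerns a secondary pilot comparison and does not threaten the study's main conclusion.

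**What to change.** In D11, write SUS for USAS and replace the independent-samples test with a paired-samples t-test on the within-dyad SUS difference (parent minus adolescent), reported with the mean difference and its 95% confidence interval.

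State how the effect size is standardised, since the two usual choices differ: 0.6 in raw-score SD units is 0.6/√(2 × (1 − 0.3)) = 0.51 in difference-score SD units at r = 0.3.

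If some dyads have only one SUS score, use a model whose within-dyad residual covariance is unstructured or compound-symmetric and may be negative. A plain dyad random intercept cannot represent negative correlation. At r = -0.2 with 24 dyads its variance is truncated to zero in about 83% of samples, and type I error is about 6.9% (on 23 df). At r = 0.1 and 0.3 it is about 5.3% and 5.0%, so this detail matters only if the correlation is negative.

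The cost is one or two sentences and no new data. The downside is the smaller degrees of freedom, about 2 points of power (53% against 51% with 24 dyads) if the true correlation is zero.

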## **E. PROTECTION OF HUMAN SUBJECTS**

### **E1. RISKS TO THE SUBJECTS**

#### *a. Human Subjects Involvement and Characteristics*

- Describe the proposed involvement of human subjects.

- Describe the characteristics of the subject population, including their anticipated number, age range and health status.

Three categories of human subjects will participate: 1) Parents of adolescents who are receiving mental health treatment, 2) adolescents receiving mental health treatment, and 3) therapists providing mental health treatment to parents and adolescents jointly. Participants will include at least 24 parents and 24 youth (at least 4 each in the field-based beta testing phase, 20 each in the Open Trial). Depending on problems encountered during the field test phase of the study, additional parents and youth might be needed to “debug” app problems prior to the open trial. The maximum number of parent and youth enrollees will not exceed 30 of each. Estimating therapist enrollment is difficult, because it is not yet known how many therapists will need to enroll in order to recruit a minimum of  $N = 24$  parent-youth dyads. We assume that a maximum  $N = 40$  enrolled therapists will be sufficient to recruit the parent-youth sample.

Parent and therapist age ranges will vary, but all will be adults (age 18 or older). Youth participants will range in age from 12-17 years old. All participants are expected to be physically healthy. In terms of mental health functioning, adolescent participants will be heterogenous, but all will have functional impairments sufficient to warrant their participation in either in-home or outpatient mental health treatment. Functional impairments may include internalizing symptoms (e.g., depressed mood, anxiety, social withdrawal), externalizing symptoms (e.g., oppositional behavior, drug or alcohol use), and failure to meet the developmental demands of their natural environments (e.g., to attend school, interact appropriately with peers, or refrain from criminal activity). A unifying factor across this heterogenous sample of adolescents is that all will be receiving family-oriented mental health treatment in which one goal is improved parental management of adolescent behavior.

Parent participants will likely be experiencing some distress caused by factors related to the adolescents' need for mental health treatment. Some may have mental health symptoms of their own (e.g., depression, anxiety). Therapist participants are not expected to be experiencing any distress or symptoms.

Parent and youth participants will be asked to download and use a new mobile phone application designed to help them meet one of their treatment goals, namely, better parental management of youth behavior. Participants will use the app as they wish over a 2- or 6-week testing period, and app usage data will be obtained. They will participate in pre- and post-usage assessment sessions and an exit interview post-usage. After receiving training, therapist participants will be asked to help parents set up the behavioral management feature of the app

as part of a regularly-scheduled treatment session and to offer the parent help using the app if desired. Once the app use testing period is over for their linked parent-youth dyad, therapists will answer questionnaires about the technology and participate in a qualitative exit interview.

## E2. Targeted Enrollment

### Targeted/Planned Enrollment Table

Total Planned Enrollment 108

TARGETED/PLANNED ENROLLMENT: Therapists (n = 40)			
Ethnic Category	Sex/Gender		
	Females	Males	Total
Hispanic or Latino	5	2	7
Not Hispanic or Latino	25	8	33
Ethnic Category: Total of All Subjects*	40		
Racial Categories			
American Indian/Alaska Native	0	0	0
Asian	1	1	2
Native Hawaiian or Other Pacific Islander	0	0	0
Black or African American	6	2	8
White	25	5	30
Racial Categories: Total of All Subjects*	32	8	40

*\*The "Ethnic Category: Total of All Subjects" must be equal to the "Racial Categories: Total of All Subjects".*

In outpatient and in-home therapy settings, higher portions of mental health therapists tend to be female than would be expected by chance.

TARGETED/PLANNED ENROLLMENT: Parents (n = 24)			
Ethnic Category	Sex/Gender		
	Females	Males	Total
Hispanic or Latino	4	1	5
Not Hispanic or Latino	18	1	19
Ethnic Category: Total of All Subjects*	24		
Racial Categories			
American Indian/Alaska Native	0	0	0
Asian	1	1	2
Native Hawaiian or Other Pacific Islander	0	0	0
Black or African American	3	1	4
White	15	3	18
Racial Categories: Total of All Subjects*	19	5	24

Mothers tend to participate in the mental health treatment of adolescents more often than fathers. This phenomenon is due to several factors, including the cultural expectation that mothers (not fathers) are the primary caretakers of children; mothers less likely to face employment barriers to participation in treatment than are fathers; and single-parent households tend to be female-headed. Thus, parent participants are expected to be predominantly female.

Because an inclusionary criteria for the study is that the parent be English-language fluent (this preliminary version of the app exists only in English at this time), fewer Hispanic participants are expected than would be by chance.

TARGETED/PLANNED ENROLLMENT: Adolescents (n = 24)			
Ethnic Category	Sex/Gender		
	Females	Males	Total
Hispanic or Latino	1	3	4
Not Hispanic or Latino	8	12	20
Ethnic Category: Total of All Subjects*	24		
Racial Categories			
American Indian/Alaska Native	0	0	0
Asian	1	1	2
Native Hawaiian or Other Pacific Islander	0	0	0
Black or African American	1	4	5
White	3	14	17
Racial Categories: Total of All Subjects*	5	19	24

More boys than girls are referred for mental health treatment, and are referred more commonly than girls for a problem involving poor parental management of youth behavior.

- Identify the criteria for inclusion or exclusion of any subpopulation.
- Explain the rationale for the involvement of special classes of subjects, such as fetuses, neonates, pregnant women, children, prisoners, institutionalized individuals, or others who may be considered vulnerable populations. Note that 'prisoners' includes all subjects involuntarily incarcerated (for example, in detention centers) as well as subjects who become incarcerated after the study begins.
- If you propose to exclude any sex/gender or racial/ethnic group, include a compelling rationale for the proposed exclusion. For example, 1) the research question addressed is relevant to only one gender or 2) evidence from prior research strongly demonstrates no difference between genders.
- Provide either a description of the plans to include children or, if children will be excluded from the proposed research, then you must present an acceptable justification for the exclusion. For example, 1) the condition is rare in children as compared to adults or 2) insufficient data are available in adults to judge risk in children.
- List any collaborating sites where human subjects research will be performed, and describe the role of those sites in performing the proposed research.

### **E3. Rationale for the Inclusion of Children under the age of 18**

Participation of youth is critical, as the aims of the study are to test a technology that is designed to improve parent management practices with youth receiving mental health treatment. The study also seeks to determine whether app components designed for youths themselves are appealing to youth.

### **E4. Collaborating Sites**

Six sites have agreed to allow the PI to recruit participants within their organizations. These sites are: 1) Advanced Behavioral Health (ABH, Connecticut); 2) Catholic Charities (upstate New York); 3) Children's Village (upstate New York and New York City); 4) the Maryland Innovations Institute (Maryland); 5) the Portland Dialectical Behavior Therapy Institute (PDBTI); and 6) the University of Washington Public Behavioral Health Justice Policy Institute. Therapists working within these organizations will be recruited using work email addresses provided by the organization. Parents and adolescents receiving mental health services from

these organizations will be exposed to study recruitment materials by enrolled therapist participants. Parent and youth research activities will take place almost exclusively within their homes and other natural settings, with the exception that these participants may watch a recruitment video following a treatment session while in the treatment provider organization's facility, and may discuss the app with their therapist for clinical purposes.

Although these collaborating organizations will be instrumental in helping study staff recruit participants, their involvement will not rise to the level of "engaged in research activities," as defined by the federal Office of Human Research Protections (OHRP). Per OHRP guidelines set forth at <http://www.hhs.gov/ohrp/policy/engage08.html>, an institution is considered *engaged* in a research project when its employees: (1) collect data about the subjects of the research through intervention or interaction with them; (2) collect identifiable private information about the subjects of the research; or (3) conduct the informed consent process with human subjects. In the present study, staff at participating organizations will **not** be conducting any of these activities. Further, OHRP guidelines state specifically that merely making referrals of potential participants to research projects or otherwise assisting with participant recruitment does not elevate to the level of research engagement (see *OHRP Guidance on Engagement of Institutions in Human Subjects Research*, Section III, B4).

The Evidence-Based Practice Institute (EBPI) is a collaborating site in this research; [name], EBPI's Chief Scientific Officer, is a Co-PI on the grant that funds this research. She and several other EBPI staff serve as research staff on this study, and EBPI maintains the app server. All EBPI staff involved in this study have completed all MUSC IRB-required CITI training modules and are included as MUSC study staff in this application. The IRB with whom EBPI is enrolled, the Behavioral Health Research Consortium (BHRC), will also review this application. No study procedures will commence until both the MUSC and BHRC IRBs approve all study procedures.

